	 Eligible to receive low-dose cytarabine treatment ECOG performance status ≤ 2 Female patients of childbearing potential and males must agree to use adequate contraception (e.g., hormonal or barrier method of birth control; abstinence) for the duration of study treatment and for 6 months after the last dose of Cytarabine or 3 months after last dose of GRASPA (whichever is the longest). Negative serum pregnancy test at study entry for female subjects of childbearing potential Subscription to social security insurance (if applicable, in accordance with local regulations) Ability to understand, and willingness to sign, a written informed consent document and to comply with scheduled visits, treatment plans, laboratory tests, and other study procedures 						
Main Exclusion Criteria	 Patients with M3 AML of FAB classification (APL, acute promyelocytic leukemia) Patients with AML involving chromosome 16 abnormalities or translocation (8:21) (CBF-AML) Patient with secondary AML subsequent to prior malignant blood disorder such as: Myelodysplastic syndrome diagnosed more than 6 months before study entry Myeloproliferative syndrome 						
	 Prior therapy to AML (standard therapy or investigational agents) Inadequate organ function : Uncontrolled or severe cardiovascular disease including myocardial infarction within 6 months of enrollment, New York Heart Association (NYHA) Class III or IV heart failure, uncontrolled angina, clinically significant pericardial disease, or cardiac amyloidosis. Serum creatinine concentration > 2 x ULN (Upper Limit of Normal) AST or ALT levels > 3.5xULN or 5xULN if related to AML Total bilirubin > 2 x ULN INR > 1.5, unless patient under chronic treatment with anticoagulants (in this case, INR should be within expected ranges for the specific condition) Insulin-dependent or uncontrolled diabetes mellitus Concurrent malignancies other than AML requiring chemotherapy Severe active infection, HIV seropositivity, or known active type B or C viral hepatitis Known or suspected hypersensitivity or intolerance to mannitol Breastfeeding or lactating women 						
Location	EUROPE						

- CONFIDENTIAL -

Study duration	Each patient will be followed for 24 months in the study.								
Study Treatment	In the experimental group, the patients will receive one injection of GRASPA (100 IU/kg) in combination with subcutaneous low-dose cytarabine (same posology as reference group hereafter), every 28 days.								

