11.1.2.2 Recording procedure

Any event meeting the definition of an AE / SAE must be collected and reported from subject signature of the informed consent and until 4 months after last GRASPA/ low-dose cytarabine administration (see Figure 4).

Any AE / SAE related to GRASPA according to investigator's opinion must be collected and reported throughout study duration.

Any SAE leading to death or life threatening must be collected and reported throughout study duration. **Figure 4: Safety reporting timeline guide**

All AE / SAE must be followed until resolution or the end of the protocol. The Investigator should ensure that adequate medical care is provided to the subject for any adverse event.

If there are several events and different symptoms combined to a main AE, then the only main AE (diagnostic preferable if available) should be recorded in the CRF. Where there is no link between different clinical symptoms occurring at the same time, each sign should be recorded as separate AE.

Occurrence and follow-up of AE should be assessed at each visit, and essential data listed hereafter should be recorded in the patient's CRF and patient's medical file as well:

- the severity or grade of the adverse event,
- the causality: determination of whether an adverse event is related to the investigational treatment or procedure, or other agents are suspected of causing the adverse event,
- the action(s) taken regarding investigational product (continued / interrupted / stopped)
- the corrective treatment if any
- the event outcome
- the seriousness of the event

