5.8.1. Adverse Events

Safety and tolerability will be assessed in terms of AEs, SAEs, laboratory data and vital signs, which will be collected for all subjects. The AE term (Investigator term) will be assigned to the lowest level term (LLT), and a preferred term (PT) will be classified by a high level term (HLT), a high level group term (HLGT) and a system organ class (SOC) according to the Medical Dictionary for Regulatory Activities (MedDRA) thesaurus, Version 15.1 or higher depending on the latest version available during the study. The intensity of AEs will be graded according to the NCI-CTCAE (version 4.0).

An overview of the number of patients with AEs and the corresponding number of AEs will be presented through tables and listings:

- Total AE count
- Any AE
- Any treatment-related AE (Cytarabine and/or GRASPA®)
- Any AE of CTCAE grade ≥ 3
- Any AE of CTCAE grade = 4
- Any treatment-related (Cytarabine and/or GRASPA®) AE of CTCAE grade ≥ 3
- Any severe treatment-related (Cytarabine and/or GRASPA®) AE
- Any AE with outcome of death
- Any serious AE

- Any treatment-related (Cytarabine and/or GRASPA®) serious AE
- Any AE leading to permanent discontinuation
- Any treatment-related (Cytarabine and/or GRASPA®) AE leading to permanent discontinuation (Action taken=Withdrawn)
- Any AE leading to temporary discontinuation
- Any treatment-related (Cytarabine and/or GRASPA®) AE leading to temporary discontinuation (Action taken=Reduced)

An AE will be considered as “treatment-related” if the relationship to study treatment is ticked “possible,” “probable” or “certain/definite”.

For subject counts, subjects are included only once, even if they experienced multiple events in that category.

All the following summaries will be displayed by treatment groups on the safety population:

- All AE by System Organ Class (SOC) term, Preferred Term (PT)
- AE Experienced by $\geq 5\%$ of Subjects by SOC term and PT
- Treatment-related (Cytarabine and/or GRASPA®) AE by SOC term and PT
- AE of CTCAE grade ≥ 3 by SOC term and PT
- AE of CTCAE grade = 4 by SOC term and PT
- Treatment-related (Cytarabine and/or GRASPA®) AE of CTCAE grade ≥ 3 by SOC term and PT
- Severe treatment-related (Cytarabine and/or GRASPA®) AE by SOC term and PT
- AE with outcome of death
- Serious AE
- Treatment-related (Cytarabine and/or GRASPA®) serious AE
- AE leading to permanent discontinuation
- AE leading to temporary discontinuation

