14.2.1.3.1.2	Summary of Progression Free Survival by Treatment Group	PP
14.2.1.3.2.1	Progression Free Survival by Treatment Group – Kaplan Meier Curves	ITT

Table/Figure Number	Output Title	Analysis Set
14.2.1.3.2.2	Progression Free Survival by Treatment Group – Kaplan Meier Curves	PP
14.2.1.3.3.1	Summary of Progression Free Survival by Treatment Group – Cox PH Model with Prognostic Factors	ITT
14.2.1.3.3.2	Summary of Progression Free Survival by Treatment Group – Cox PH Model with Prognostic Factors	PP
14.2.1.3.4.1	Forest Plot of Progression Free Survival Odds Ratios – Subgroup Analyses	ITT
14.2.1.3.4.2	Forest Plot of Progression Free Survival Odds Ratios – Subgroup Analyses	PP
14.2.1.4.1	Summary of Relapse Free Survival by Treatment Group	ITT
14.2.1.4.2	Relapse Free Survival by Treatment Group – Kaplan Meier Curves	ITT
14.2.1.5	Summary of Transfusion Needs by Treatment Group	ITT
14.2.1.6.1	Summary of Biomarkers	ITT
Figure 14.2.1.6.2	Biomarkers Over Time – Spaghetti Plots	ITT
	PK and PD Parameters	
14.2.9.1	PK and PD Parameters – Plasma and Blood – Summary Statistics Over Time	Safety

Table/Figure Number	Output Title	Analysis Set
14.2.9.2	PK and PD Parameters – Plasma and Blood – Patients with Asparagine Depletion	Safety
14.2.9.3	PK and PD Parameters – Immunogenicity	Safety
14.2.9.4	Summary of Biomarker Cytogenetic Testing	Safety
14.2.9.5	Summary of Bone Marrow Tumor Cell Parameters	Safety
	Quality of Life Questionnaires	
14.2.10	QLQ-C30 Absolute and Changes From Baseline	ITT
	Number of Hospitalizations	
14.2.11	Summary of Hospitalizations by Treatment Group	ITT
	Safety Data	
	Adverse Events	
14.3.1.1.1	Summary Analysis of Incidence of Treatment Emergent Adverse Events	Safety
14.3.1.1.2	Summary Analysis of Incidence of Treatment-Related Treatment Emergent Adverse Events	Safety
14.3.1.1.3	Summary Safety Analysis of GRASPA in combination with low-dose cytarabine	ITT

Table/Figure Number	Output Title	Analysis Set
14.3.1.2.1	Incidence of Treatment Emergent Adverse Events by Preferred Term	Safety
14.3.1.2.2	Incidence of Treatment Related Treatment Emergent Adverse Events by Preferred Term	Safety
14.3.1.2.3	Incidence of Treatment Emergent Adverse Events with Toxicity Grade of 3 or 4 by Preferred Term	Safety
14.3.1.2.4	Incidence of Treatment Related Treatment Emergent Adverse Events with Toxicity Grade of 3 or 4 by Preferred Term	Safety
14.3.1.2.5	Incidence of Treatment Emergent Serious Adverse Events by Preferred Term	Safety

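### By-arm adverse event tables use crude percentages with no time-at-risk denominator, and late GRASPA-related events can enter the treatment-related rows from one arm only

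*SAP*

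**What the plan says.** Protocol 11.1.2.2 sets three collection windows. Any AE or SAE is collected from consent "until 4 months after last GRASPA/ low-dose cytarabine administration", in both arms. Then: "Any AE / SAE related to GRASPA according to investigator's opinion must be collected and reported throughout study duration". And, whatever the cause: "Any SAE leading to death or life threatening must be collected and reported throughout study duration". Study duration is fixed: "Each patient will be followed for 24 months in the study". No sentence extends the window for cytarabine-related events.

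On analysis, SAP 5.8.1 states: "All the following summaries will be displayed by treatment groups on the safety population". It plans counts of patients and of events, with the convention "For subject counts, subjects are included only once, even if they experienced multiple events in that category". One overview row is "Any treatment-related AE (Cytarabine and/or GRASPA"), which pools relatedness to either drug. The special-interest shell in the same section is n (%) plus a raw number of events.

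The output list in SAP 8.1 uses titles such as "Summary Analysis of Incidence of Treatment Emergent Adverse Events". The SAP gives neither a start nor an end for treatment-emergent. Exposure and study duration have their own tables (14.1.6.1 and 14.1.6.2.1) but are not used in any AE summary.

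**The concern.** Under Protocol 8.11, study treatment generally stops at relapse or resistant disease. The general AE window closes 4 months after the last dose, or earlier at death, so its length depends on efficacy. An arm with better disease control is watched for longer and will show a higher crude percentage even if the monthly risk is identical. An arm in which toxicity ends treatment early is watched for less time, and its percentage is flattered. Raw event totals are harder still to compare, with 41 patients planned on low-dose cytarabine (LDAC) and 82 on GRASPA plus LDAC.

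The second problem is narrower. Once the general window has closed, the only events below life-threatening severity that must still be collected are those judged GRASPA-related, and these can arise only in the GRASPA arm. They then fall into the pooled treatment-related rows. The trial is open label, so relatedness is judged with the arm known. Protocol 11.1.2.4 has events of unassessable causality reported as possibly related, and SAP 5.8.1 counts possible as related. A late event of unclear cause can therefore count in the GRASPA arm when the same event under LDAC need not be collected.

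Safety of the combination is a stated secondary objective, and SAP section 1 says the results will inform a decision on phase 3.

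**Working it through.** **Step 1. Windows side by side (Protocol 11.1.2.2).**

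| Events | LDAC | GRASPA + LDAC |
|---|---|---|
| All-cause AE/SAE | consent to last dose + 4 months | same rule |
| Fatal or life-threatening SAE, any cause | to end of study | same rule |
| Judged related to a study drug, less than life-threatening | last dose + 4 months | last dose + 4 months; to end of study if GRASPA-related |

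Only the last row differs by rule. The first differs in length whenever treatment duration or survival differs.

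**Step 2. Inputs.** The documents give no AE rate, so there is no stated figure to reproduce. The following is an illustration.
- Median PFS 2 vs 3.5 months (SAP 5.1), standing in for time on treatment. Protocol 15.3.1 attaches these figures to survival; I follow SAP 5.1.
- Median OS 6.4 vs 8.0 months, the SAP section 1 illustration of a hazard ratio of 0.8.
- A tail of 4 months and a cap at 24 months, from the protocol.
- Assumed: a constant first-event hazard r of 0.02, 0.05, 0.10 or 0.20 per month, equal in both arms, and exponential times.

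**Step 3. Formula.** The window is W = min(T + 4, D, 24), with T the time on treatment and D the time to death. The crude percentage is P = 1 − E[exp(−rW)]. The dependence between T and D is not in the documents, so I used three versions:
- (i) Death and progression are competing exponential hazards, and T is whichever comes first. With a = ln2/OS + r and b = ln2/PFS + r, P = r × [(1 − e^(−4a))/a + e^(−4a)(1 − e^(−20b))/b].
- (ii) T and D are independent. The formula is the same with b = ln2/OS + ln2/PFS + r.
- (iii) An independent exponential survival time follows progression, with mean (OS − PFS)/ln2. This was integrated numerically.

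**Step 4. Version (i) at r = 0.10.**
- LDAC: a = 0.1083 + 0.10 = 0.2083 and b = 0.3466 + 0.10 = 0.4466. P = 0.10 × (2.714 + 0.973) = 36.9%.
- GRASPA + LDAC: a = 0.0866 + 0.10 = 0.1866 and b = 0.1980 + 0.10 = 0.2980. P = 0.10 × (2.818 + 1.586) = 44.0%.

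**Step 5. Results, LDAC vs GRASPA + LDAC, with the excess in percentage points.**

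| r per month | (i) | (ii) | (iii) |
|---|---|---|---|
| 0.02 | 9.5 vs 12.4 (2.9) | 8.8 vs 10.8 (2.0) | 10.9 vs 14.3 (3.4) |
| 0.05 | 21.5 vs 27.0 (5.5) | 20.1 vs 24.0 (4.0) | 24.5 vs 31.0 (6.5) |
| 0.10 | 36.9 vs 44.0 (7.2) | 35.0 vs 40.5 (5.5) | 41.8 vs 50.2 (8.4) |
| 0.20 | 56.6 vs 63.6 (6.9) | 54.9 vs 60.7 (5.8) | 63.6 vs 71.5 (8.0) |
| Mean window, months | 5.1 vs 6.9 | 4.7 vs 5.9 | 5.9 vs 8.0 |

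The excess runs from 2.0 to 8.4 points although the true rates are equal.

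**Step 6. What a rate does.** In step 4 the bracketed sums, 3.687 and 4.405 months, are the mean times at risk to first event. First events over time at risk give 0.3687/3.687 = 0.10 and 0.4405/4.405 = 0.10, a ratio of 1.00.

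**Step 7. Late period.** In version (i), mean survival up to month 24 is (1 − e^(−24·ln2/OS))/(ln2/OS), or 8.5 and 10.1 months. Subtracting the mean windows leaves about 3.4 months (LDAC) and 3.2 months (GRASPA + LDAC) per patient. In that time only the GRASPA arm can add events below life-threatening severity. The documents give no rate for such events, so I put no figure on this part.

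**The case against.** Several points on the other side are sound. Counting a patient once per category is ordinary practice, and that sentence by itself is no error. Exposure, dose intensity and study duration are tabulated. Deaths within 28 days of last administration have a fixed window. Serious and fatal AEs, and those leading to discontinuation, are listed with onset dates. No hypothesis test on AEs is planned. Output shells are in a separate document, so treatment-emergent may be defined there; only its absence from the SAP can be asserted. None of this corrects the by-arm percentages: a reader who has the exposure table still cannot turn a crude percentage into a rate.

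Three stronger readings are tempting and should not be made.
- A reader might infer that every event not attributed to GRASPA stops being collected 4 months after the last dose. Protocol 11.1.2.2 keeps fatal and life-threatening SAEs open throughout, in both arms.
- A reader might infer that the all-cause windows differ by design. The rule is common to both arms. Protocol 8.11 also lists toxicity, patient refusal and lack of benefit as reasons to stop, and allows treatment beyond progression, so neither the direction nor the size of any difference is settled.
- A reader might take on-treatment time alone, with means 2/ln2 = 2.885 and 3.5/ln2 = 5.049 months. Then rm/(1 + rm) gives 12.6% vs 20.2% at r = 0.05 and 36.6% vs 50.2% at r = 0.20, an excess of 7.5 to 13.7 points. That leaves out the 4-month tail and death, and overstates the effect.

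The illustration also takes both assumed benefits as real. With median OS at 6.4 months in both arms, the excess falls to 2.2 to 4.8 points in version (i) and 1.1 to 2.9 in version (ii).

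**Conclusion.** The concern holds in this limited form. The planned AE comparison has no time-at-risk denominator, and one class of events (late, judged GRASPA-related, less than life-threatening) can reach the pooled treatment-related rows from the GRASPA arm only. If the PFS and OS medians in the SAP came true, window length alone would produce an excess of about 2 to 8 percentage points in that arm. The AE hazards, their equality and constancy, the exponential times and the link between PFS and OS are my assumptions. If GRASPA shortened treatment, the distortion would run the other way and hide toxicity. The open-label relatedness asymmetry comes on top and cannot be sized from the documents. The primary OS analysis is not affected. This is a cheap improvement to a stated safety comparison, worth making before database lock.

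**What to change.** In SAP 5.8.1:
- Define treatment-emergent, identically in both arms, as onset from first study dose to 4 months after the last dose of any study drug. Use it for every by-arm AE table, including the treatment-related rows.
- Put later events in a separate table or listing by arm: GRASPA-related events, and fatal or life-threatening SAEs of any cause, so that the latter are not lost from the report.
- Beside the crude percentages, give first events per patient-month at risk for all, grade 3 or higher, serious and special-interest AEs. The common definition gives one rule but not equal lengths, so the rates are still needed.

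The text on follow-up contact should be aligned at the same time: SAP 5.2.9 has a safety call every 4 months after treatment, while Protocol 8.10 has one at 4 months.

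The change uses onset and dosing dates already planned for collection and listing, and needs no new data. The cost is SAP wording and larger tables. A rate per patient-month summarises best when the hazard is roughly constant, so the crude percentages should stay alongside it.

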8.11 End of study treatment

Patients will stop study treatment in following situations:

- Disease relapse or presence of a resistant disease, unless the investigator considers that the patient has a clinical benefit from continuing the treatment. In this case, the investigator should continue to perform the same study visits as long as considered clinical beneficial.
- Occurrence of GRASPA-related toxicity, such as:
 - Grade 3 or 4 pancreatic toxicity
 - o Grade 3 or 4 hepatic toxicity, allergic reaction, or coagulation event
 - o other non-hematologic Grade 4 toxicity

Patient assessment should continue as planned until evidence of relapse or presence of a resistant disease, in which case, patient will be followed up for survival.

- Patient unwilling to continue
- No evidence of study treatment benefit at investigator's decision

9. Investigational product: GRASPA

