11.1.2 Collection, recording and reporting of AE

11.1.2.1 Collection of Adverse Events

The following AE will be taken into account for this trial (grading reference used is the NCI-CTCAE version 4.0):

Any event will be recorded, irrespectively of the relationship with GRASPA / low dose cytarabine according investigator's opinion AND the grade. Similarly, any reaction linked to red blood cells (see section 11.3) during GRASPA administration will be recorded as an AE in the CRF.

Laboratory tests abnormalities

Any abnormal laboratory value should be reported as an AE.

- EXCEPTION: When ALL the following criteria, the investigator may decide not to be reported such the abnormal value:
 - The abnormal parameter IS part of the schedule of assessment AND
 - Is NOT associated with clinical symptoms AND
 - Is considered NOT medically significant by the Investigator, AND
 - Does NOT result in change of GRASPA / Low-dose cytarabine or other concomitant treatment administration

Disease Progression

In this study, the signs and symptoms corresponding to the disease progression or worsening (AML) **should not be recorded as AEs**. Death related to disease progression should not be reported as SAE.

The following should not be recorded as AEs, if recorded at screening:

- Pre-planned procedure, unless the condition for which the procedure was planned has worsened from the first trial related activity after the subject has signed the informed consent.
- Pre-existing stable conditions found as a result of screening procedures. Worsening of preexisting conditions must be reported.

If seriousness criterion is met, a SAE should be declared to ERYTECH Pharma drug safety, completing SAE report form (see section 11.2 and Appendix 7).

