Serious AE, AE with outcome of death and AE leading to permanent or temporary discontinuation will also be described on an individual basis: treatment group, patient's code, sex and age, investigator's reported term, preferred term, date of onset, NCI-CTCAE Criteria Grading, intensity, outcome, seriousness, suspected relationship regarding Cytarabine and GRASPA®, action taken, corrective therapy.

A special focus will be put on diabetogenic and pancreatic adverse events based on the following table:

	GRASPA + LDAC n(%)	LDAC n(%)	Total n(%)
Number of patients with xxx adverse events	xx (x.x%)	xx (x.x%)	xx (x.x%)
PT1	x (x.x%)	x (x.x%)	x (x.x%)
PT2	x (x.x%)	x (x.x%)	x (x.x%)
Number of events	xx	xx	xx
Events characteristics, n			
Serious	x (x.x%)	x (x.x%)	x (x.x%)
Cytarabine-related	x (x.x%)	x (x.x%)	x (x.x%)
GRASPA®-related	x (x.x%)	x (x.x%)	x (x.x%)
Permanent discontinuation of Cytarabine	x (x.x%)	x (x.x%)	x (x.x%)
Permanent discontinuation of GRASPA	x (x.x%)	x (x.x%)	x (x.x%)
Fatal	x (x.x%)	x (x.x%)	x (x.x%)
Number of occurrences, n			
One	x (x.x%)	x (x.x%)	x (x.x%)
Two or more	x (x.x%)	x (x.x%)	x (x.x%)
Maximum toxicity grade, n			
Grade 1	x (x.x%)	x (x.x%)	x (x.x%)
Grade 2	x (x.x%)	x (x.x%)	x (x.x%)
Grade 3	x (x.x%)	x (x.x%)	x (x.x%)
Grade 4	x (x.x%)	x (x.x%)	x (x.x%)
Outcome, n			
Resolved	x (x.x%)	x (x.x%)	x (x.x%)
Not resolved	x (x.x%)	x (x.x%)	x (x.x%)
Fatal	x (x.x%)	x (x.x%)	x (x.x%)
Action taken with cytarabine, n			
Dose not changed	x (x.x%)	x (x.x%)	x (x.x%)
Temporarily interrupted	x (x.x%)	x (x.x%)	x (x.x%)
Permanently discontinued	x (x.x%)	x (x.x%)	x (x.x%)
Not applicable	x (x.x%)	x (x.x%)	x (x.x%)
Action taken with GRASPA®, n			
Dose not changed	x (x.x%)	x (x.x%)	x (x.x%)
Temporarily interrupted	x (x.x%)	x (x.x%)	x (x.x%)
Permanently discontinued	x (x.x%)	x (x.x%)	x (x.x%)
Not applicable	x (x.x%)	x (x.x%)	x (x.x%)

Diabetogenic effects will comprise diabetes mellitus, glucose and lipid increase. Pancreatic events will comprise clinical pancreatitis and asymptomatic (biochemical) pancreatitis.

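### The special-focus safety table counts silent pancreatic, glucose and lipid findings from reported AEs only, so it can miss some, mainly at Grade 1–2, and the shortfall can differ by arm

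*SAP*

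**What the plan says.** SAP 5.8.1 introduces the table in these words: "A special focus will be put on diabetogenic and pancreatic adverse events based on the following table". The shell shows preferred terms, seriousness, relation to each drug, action taken, outcome and maximum toxicity grade from 1 to 4. The terms start from the investigator's wording and are then coded in MedDRA. Two sentences below the shell define the content: "Diabetogenic effects will comprise diabetes mellitus, glucose and lipid increase" and "Pancreatic events will comprise clinical pancreatitis and asymptomatic (biochemical) pancreatitis". No threshold is given for lipase, amylase, glucose or lipids, and no rule brings laboratory values into the count.

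Protocol 11.1.2.1 sets the default: "Any abnormal laboratory value should be reported as an AE". It then allows an exception under which "the investigator may decide not to be reported such the abnormal value". Four conditions must all be met. The parameter is scheduled, there are no symptoms, and the investigator regards the value as medically unimportant. The last condition is that the value "Does NOT result in change of GRASPA / Low-dose cytarabine or other concomitant treatment administration".

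Protocol 8.7.1 schedules glucose, cholesterol, triglyceride, lipase and amylase in both arms. Protocol 6.1 describes an open-label trial.

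Laboratory results also have their own outputs. SAP 5.8.2.1 describes each parameter by arm and time point and identifies patients with Grade 3 or 4 values. The table list in SAP 8.1 adds a biochemistry shift from baseline to the worst later result.

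**The concern.** A biochemical event without symptoms is the kind of finding the reporting exception covers. If the investigator uses the exception, the event leaves no AE term and drops out of the one table that is meant to focus on it. The decision is made by someone who knows the treatment. In addition, one of the changes that makes a value reportable, a change of GRASPA, can occur only in arm B.

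The displayed rates would then reflect reporting habits as well as toxicity. Pancreatic toxicity and hyperglycemia are among the safety outcomes singled out in Protocol 4.3.2 and SAP 3.5.3 (at Grade 3 or 4), and this table is where a reader would look for the comparison between arms.

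**Working it through.** **Step 1. Apply the four conditions to a silent rise in lipase, amylase, glucose or lipids.**

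| Condition in Protocol 11.1.2.1 | Met? | Can it differ by arm? |
|---|---|---|
| Scheduled parameter | Yes, for all of them (Protocol 8.7.1) | No |
| No symptoms | Yes, if the event is purely biochemical | No |
| Regarded as medically unimportant | Investigator's judgement, arm known | Possibly |
| No change to GRASPA, cytarabine or other treatment | Depends on the case | GRASPA part: arm B only. Other parts: both arms |

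Two conditions are met by the nature of the event. Whether it is reported then turns on the other two.

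**Step 2. Locate the gap by grade.** The end-of-treatment list in Protocol 8.11 includes "Grade 3 or 4 pancreatic toxicity" among GRASPA-related toxicities. Protocol 9.5 refers to Grade 4 pancreatitis. A value that stops GRASPA must be reported, and Grade 3/4 values are picked up from the laboratory data in any case. The exception therefore matters mainly at Grade 1–2, for which the focus table has its own rows.

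**Step 3. Reproduce the only rate in the documents for this type of event.** Protocol Table 2 (earlier ALL trial) gives amylase and/or lipase elevation as 7/26 = 26.9% on GRASPA and 15/28 = 53.6% on native asparaginase. Both reproduce. Protocol 5.2.1 calls the same 26.9% asymptomatic pancreatitis.

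**Step 4. Illustrate, with assumed reporting shares.** Let p be the true rate and s the share of cases reported.

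- Displayed rate = p × s
- Displayed ratio (B/A) = (pB / pA) × (sB / sA)

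Take 82 patients in arm B and 41 in arm A (Protocol 15.2), and p = 7/26 in both arms. The expected true counts are 82 × 7/26 = 22.1 and 41 × 7/26 = 11.0.

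| sB | sA | Arm B | Arm A | Ratio |
|---|---|---|---|---|
| 100% | 100% | 22.1/82 (26.9%) | 11.0/41 (26.9%) | 1.0 |
| 50% | 50% | 11.0/82 (13.5%) | 5.5/41 (13.5%) | 1.0 |
| 100% | 50% | 22.1/82 (26.9%) | 5.5/41 (13.5%) | 2.0 |
| 50% | 100% | 11.0/82 (13.5%) | 11.0/41 (26.9%) | 0.5 |

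With an assumed control rate of 10%, the true ratio is 26.9/10 = 2.7. The displayed ratio then runs from 2.69 × 0.5 = 1.3 to 2.69 × 2 = 5.4.

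Equal under-reporting lowers both rates and leaves the ratio alone. Only unequal reporting distorts the comparison, and it can do so in either direction. A count taken from the recorded laboratory values does not contain s at all.

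**The case against.** The case against giving this much weight is substantial.

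- **The default is to report.** The exception is optional and needs all four conditions.
- **The laboratory data are analysed separately.** Values by arm, Grade 3/4 patients and worst-value shifts appear whatever was reported as an AE. This largely stands. Two small gaps remain. SAP 5.8.2.1 lists lipase and amylase under a pancreas heading of their own, and SAP 8.1 names no pancreas shift table. Protocol 8.7.1 classes them as chemistry, so the biochemistry table probably covers them, but this is not explicit. SAP 5.8.2.1 also stops at D23, although Protocol 8.7.1 and SAP 5.2.9 include D27.
- **The stopping rules are weak evidence of unequal reporting.** They apply at Grade 3/4, where a value is least likely to be dismissed in either arm. Changes to cytarabine or concomitant treatment make a value reportable in both arms. This stands. What is left is open-label judgement on lower-grade values.
- **The illustrative rates are not evidence.** The 26.9% is itself a rate of reported, study-related AEs, from ALL patients aged 1 to 55. The reporting shares and the 10% control rate have no source in the documents. This stands.
- **Most rows of the shell exist only for reported AEs.** Relatedness, action taken and outcome cannot be filled for a laboratory-derived case. This stands and shapes the fix.

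A reader might infer that the table is bound to be incomplete and to differ between arms, or that a pancreatic signal would be lost. The documents support neither inference. They do not show that the exception is used, or used unequally, and the laboratory outputs would still show the signal.

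**Conclusion.** The point holds as a possibility built into the method. The focus table takes silent laboratory findings from AE terms, the protocol permits some of those findings to go unreported, and nothing in SAP 5.8.1 fills the gap. The count can be incomplete, mainly at Grade 1–2, and can differ by arm.

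Neither direction nor size can be stated from the documents. The range of 0.5 to 2.0 around a true ratio of 1.0 follows entirely from the assumed reporting shares of 50% to 100%, and should be quoted only as an illustration.

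The weakness is confined to one descriptive safety table in a proof-of-concept trial. It does not touch the primary analysis. The change is still worth making, because it takes open-label reporting out of the focused comparison using data already collected.

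Separately, the pancreatic wording on stopping GRASPA differs between Protocol 8.11 and 9.5. The two passages must be reconciled, since they affect which arm B findings fall outside the exception. This review takes no position on which is right.

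**What to change.** In SAP 5.8.1:

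1. Add rows to the special-focus table for biochemical pancreatitis (lipase/amylase), glucose increase and lipid increase, derived from the scheduled laboratory data in both arms.
2. Define each as the patient's worst on-treatment CTCAE v4.0 grade. Use the same sampling days and the same period in each arm, and include D27. State how glucose samples are treated, since Protocol 8.7.1 does not say whether they are fasting.
3. Keep the AE-term counts, with relatedness, action taken and outcome, as separate rows, and show clinical pancreatitis on its own. Comparing the two sets of rows will show how far each arm's AE count depends on reporting.
4. Add D27 to the list of days in SAP 5.8.2.1.

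The cost is SAP wording and a derived variable. SAP section 1 requires sign-off before database lock, so the change belongs before then. There are two drawbacks. Laboratory-derived rates will be higher than AE rates and need a footnote saying why, and the AE-only rows will stay empty for laboratory-derived cases.
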